On October 24, 2012, ACIP voted to recommend Tdap for pregnant women with every pregnancy irrespective of previous Tdap history. In December 2012, the KPSC RIPC followed ACIP guidance and recommended that providers of prenatal care implement a Tdap immunization program for all pregnant women. The guidance indicated that all health-care personnel should administer a dose of Tdap during each pregnancy irrespective of the patient's prior history of receiving Tdap. In order to maximize the maternal antibody response and passive antibody transfer to the infant, optimal timing for Tdap administration was specified between 27 and 36 weeks gestation.

Prior to the conduct of this observational study of Boostrix in pregnancy, Adacel had been the only Tdap vaccine on the KPSC formulary.

Process for identifying pregnancy information

If a woman receives prenatal care at KPSC, her pregnancy is recorded in a pregnancy episode flowsheet. The flowsheet is contained in the woman's medical record and is created at the beginning of the pregnancy. It is appended with all pregnancy encounters including prenatal visits, the hospital admission for birth, as well as any post-partum visits. Pregnancy and birth information at KPSC including maternal age, pre-pregnancy height and weight, perinatal risk factors, prenatal visit information, complications of pregnancy and delivery, and procedures used during labor and delivery are available from the EHR and can be viewed in Health Connect.

Process for linking mothers and infants

As standard of care at KPSC, all infants born in KPSC hospitals are automatically assigned a MRN regardless of whether the mother is a current plan member. If the mother is a current member, the baby's MRN is automatically linked to her medical record in her pregnancy episode flowsheet.

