##### *Subgroups for endpoint-specific analysis*

For some maternal and infant AEs (endpoints), additional restriction criteria will be applied. We will exclude individuals who do not meet the restriction criteria, but not the matched pair. Analysis will be conducted on a subgroup of the population:

- Small for gestational age (SGA): Infants 1) live born, 2) singleton, and 3) born in KPSC hospitals. Rationale: The evaluation of SGA is limited to singleton births because the reference values for SGA definition are established based on singleton births. The birth weight of infants born outside KPSC hospitals is not captured in claims, and such infants are therefore excluded for this endpoint.

- Preterm delivery: Pregnant women 1) with live birth and 2) with index (vaccination) date prior to 37 weeks gestation. Rationale: Pregnant women with an index (vaccination) date on or after 37th week of gestation are not at risk of preterm delivery, and are therefore excluded for this endpoint.
- Preterm pre-labor rupture of membranes (PPROM): Pregnant women with index (vaccination) date prior to 37 weeks gestation. Rationale: Pregnant women with an index (vaccination) date on or after 37th week of gestation are not at risk of PPROM, and are therefore excluded for this endpoint.
- Transfusion during delivery hospitalization: Pregnant women with delivery hospitalization. Rationale: Transfusion can be captured by procedure codes during the delivery hospitalization.
- Stillbirth/fetal death: Pregnant women with pregnancy outcome. Rationale: Pregnant women with unknown pregnancy outcome are considered as missing data, and are therefore excluded for this endpoint.
- Neonatal death (within 28 days of birth) and congenital anomalies at birth and through 6 months of age: Infants 1) live born and 2) born in KPSC hospitals. Rationale: Infants born outside KPSC hospitals may not be captured and may not be able to be linked back to their pregnant mothers, and are therefore excluded for this endpoint.

Analysis for preeclampsia and/or eclampsia, intra-uterine infections, poor fetal growth, placental abruption, and maternal death will be conducted on all pregnant women eligible for the main analysis and descriptive analysis.

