The algorithms for identification of primary and secondary endpoints are described in the DMP. Except SGA, preterm delivery, and transfusion during delivery hospitalization, AEs identified through the algorithms will be chart reviewed to confirm the diagnosis and the onset (when applicable). Analyses of endpoints will be based on confirmed cases. For AEs with a chart-reviewed onset date, the event start date will be the onset date; for AEs without a chart-reviewed onset date (unknown or inapplicable), the event start date will be the earliest confirmed diagnosis date. To be a confirmed case, the event start date needs to be after the index date. Some AEs might be diagnosed during the delivery hospitalization, and have an event start date after the delivery date. For pre-eclampsia and/or eclampsia, intra-uterine infections, and poor fetal growth, the event date needs to be on or before the delivery date. For placental abruption and PPROM, if the event start date is after the delivery date, the delivery date will be used as the event start date.

SGA will be defined based on reference values derived by Talge et al. with a cut-off of <10th percentile (1). Talge et al used 2009-2010 US natality data and corrected for likely errors in gestational age dating to yield an up-to-date birth weight for gestational age reference. The

evaluation of SGA is limited to singleton births because the reference values for SGA definition are established based on singleton births.

Stillbirth/fetal death has a number of different and legally mandated definitions (2). This study will use ACOG's definition which defines stillbirth/fetal deaths at 20 completed weeks gestation or greater (if the gestational age is known). Maternal death will include all non-accidental deaths while pregnant or within 42 days of end of pregnancy. Neonatal death will include deaths within 28 days of birth among KPSC live born infants.

For a multiple gestation pregnancy, the pregnancy outcome will be recorded for each fetus, while the endpoint will be defined by the worst scenario. For examples, the woman will be considered to have a pre-term delivery, if any fetus was delivered pre-term after the index date. The woman will also be considered to have spontaneous abortion, therapeutic abortion, or stillbirth/fetal death if any fetus experienced these pregnancy outcomes after the index date.

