For a multiple gestation pregnancy with multiple live births, only the infant(s) with infant AEs (neonatal death and congenital anomalies) will be chart reviewed. The endpoint will be defined at the infant level.

Additional birth outcomes will be captured among KPSC born infants for descriptive purposes, but will not be considered as AEs: birth length, head circumference, and Apgar scores.

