##### 4.2 Analyses of primary endpoints

We will calculate crude incidence and 95% CI for each primary endpoint for the exposed and unexposed cohorts. Unadjusted and adjusted RR with two-sided 98.75% CI will be estimated comparing the exposed cohort to the unexposed cohort, accounting for multiple comparisons.

Analysis of primary endpoints will be used to evaluate the safety of Boostrix vaccination and concluded to be non-inferior if the upper limit of the 98.75% CI for the adjusted relative risk is below 2.

Analyses of preeclampsia and/or eclampsia and intra-uterine infection will be performed on all pregnant women eligible for main analysis. For events identified any time after the index date (e.g., preeclampsia and/or eclampsia and intra-uterine infection), the incidence will consist of the total number of women with the condition in the numerator and the total person time in the denominator. The person-year for a pregnant woman will be the time from the index date to the date of each adverse event, end of the pregnancy, or disenrollment, whichever comes first. The unadjusted and adjusted relative risk with 98.75% CI will be estimated by Poisson regression models accounting for the follow-up time without and with adjustment for potential confounders. If the outcome is common (i.e., incidence > 2%), a Poisson regression model with a robust error variance will be used to estimate the relative risk (6). The robust Poisson regression will be performed using the SAS Proc GENMOD procedure with the REPEATED statement subject= Patient\_ID.

Analysis of SGA will be performed on live singleton infants born in KPSC hospitals, while analysis of preterm delivery will be performed on pregnant women with live births, and with an index date prior to 37 weeks gestation. For events identified at delivery (e.g., SGA and preterm delivery), the incidence will consist of the total number of women or infants with the condition in the numerator and the number of women or infants for whom the condition can be assessed in the denominator. The unadjusted and adjusted relative risk with 98.75% CI will be estimated by Poisson regression models with robust error variances without and with adjustment for potential confounders. The planned methods of analysis by primary endpoint are outlined in Table 4. See Appendix A, Table Shell 4 for details.

Table 4. Analytic population and statistical methods by primary endpoint

Primary endpoints	Analytic population	Statistical Methods

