### 4.3 Analyses of secondary endpoints

The analysis of secondary endpoints will be used for hypothesis generation/signal detection. We will calculate crude incidence and 95% CI for each secondary endpoint for the exposed and unexposed cohorts. Unadjusted and adjusted RR with two-sided 95% CI will be estimated comparing the exposed cohort to the unexposed cohort. At least one case in each cohort is required to perform unadjusted and adjusted analyses. If total counts from the two groups is less than 5, then no adjusted analysis will be performed. An elevated risk will be detected if the lower limit of the 95% CI for the adjusted relative risk is above 1. The planned methods of analysis by secondary endpoint are outlined in Table 5. See Appendix A, Table Shell 4 for details.

Table 5. Analytic population and statistical methods by secondary endpoint

Secondary endpoints	Analytic population	Statistical Methods
Transfusion during delivery hospitalization	Pregnant women with delivery hospitalization	Adjusted Poisson regression model
Poor fetal growth	All pregnant women eligible for main analysis	Adjusted Poisson regression model accounting for follow up time, with robust variance estimate
Stillbirth/fetal death*	Pregnant women with pregnancy outcome	Adjusted Poisson regression model
Neonatal death	KPSC live born infants	Adjusted Poisson regression model
Maternal death	All pregnant women eligible for main analysis	Adjusted Poisson regression model accounting for follow up time
Placental abruption	All pregnant women eligible for main analysis	Adjusted Poisson regression model accounting for follow up time
PPROM	All pregnant women, with index (vaccination) date prior to 37 weeks gestation	Adjusted Poisson regression model accounting for follow up time
Congenital anomalies (CA) by type	KPSC live born infants	Adjusted Poisson regression model, with robust variance estimate if outcome is common

\*Stillbirth/fetal death will be described with or without congenital anomalies separately, but will be analyzed as one outcome.

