For poor fetal growth, placental abruption, PPROM, and maternal death, the incidence will consist of the total number of women with the condition in the numerator and the total person time in the denominator. For poor fetal growth, placental abruption, and PPROM, the person-time for a pregnant woman will be the time from the index date to the date of each adverse event, end of the pregnancy, or disenrollment, whichever comes first. For maternal death, the person-time for a pregnant woman will be the time from the index date to the date of death, 42 days after delivery, or disenrollment, whichever comes first. The unadjusted and adjusted relative risk with 95% CI will be estimated by Poisson regression models, or Poisson regression models with robust error variances if incidence >2%, accounting for the follow-up time without and with adjustment for potential confounders.

For stillbirth/fetal death and transfusion during delivery hospitalization, the incidence will consist of the total number of women with the condition in the numerator and the number of women for whom the condition can be assessed in the denominator. The unadjusted and adjusted relative risk with 95% CI will be estimated by Poisson regression models, without and with adjustment for potential confounders.

Neonatal death and congenital anomalies will be identified among infants born in KPSC hospitals. The incidence of neonatal death will be calculated as the number of neonatal deaths in the numerator and the total number of infants born in KPSC hospitals in the denominator. The prevalence of congenital anomalies (overall, by type) will be calculated as the number of infants with a congenital anomaly in the numerator and the total number of infants born in KPSC hospitals in the denominator. The proportion of live births without congenital anomalies will be calculated as 1 minus the proportion of live births with congenital anomalies among all KPSC live born infants. The unadjusted and adjusted relative risk with 95% CI will be estimated by Poisson regression models, or Poisson regression models with robust error variances if incidence >2%, without and with adjustment for potential confounders.

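### Neonatal death and congenital anomaly classes are analysed per infant with no clustering of siblings on the mother, so their 95% intervals are slightly too narrow, mainly for neonatal death.

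*SAP*

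**What the plan says.** **Unit of analysis.** For neonatal death and congenital anomalies in multiple live births, SAP 3.2.3 states: "The endpoint will be defined at the infant level". SAP 3.2.1 takes as their population all live-born infants delivered in KPSC hospitals, with no restriction to singletons. Table Shell 1 lists singletons as a subset of those infants, so multiples are in the denominator.

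**Other endpoints.** For pregnancy outcomes such as preterm delivery and stillbirth in a multiple gestation, "the endpoint will be defined by the worst scenario", giving one record per woman. For small for gestational age, "The evaluation of SGA is limited to singleton births". Neither has sibling records to cluster.

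**Variance.** SAP Table 5 gives neonatal death a plain adjusted Poisson model. For anomalies by type it gives: "Adjusted Poisson regression model, with robust variance estimate if outcome is common". The text of SAP 4.3 describes the models for both endpoints as "Poisson regression models, or Poisson regression models with robust error variances if incidence >2%, without and with adjustment for potential confounders". The trigger for robust variance is how common the outcome is, not whether records are correlated.

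**Cluster identifier.** Only SAP 4.2, on the primary endpoints, names one: "The robust Poisson regression will be performed using the SAS Proc GENMOD procedure with the REPEATED statement", with Patient_ID as the subject. It does not say whose identifier that is.

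**Decision rule.** SAP 4.3 declares an elevated risk when the lower 95% limit of the adjusted relative risk exceeds 1. SAP 4.5 then calls for a signal investigation.

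**The concern.** A model-based Poisson variance treats every infant as an independent observation. Two infants from one pregnancy share gestational age at birth, placental and maternal conditions and part of their genetics, so if one dies or has an anomaly the other is more likely to as well. The event count then varies more than the model assumes, and the interval is too short.

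Matching on multiple gestation does not cure this. It balances the share of multiples between cohorts but leaves the correlation within each pair. The SAP states that the matching variables enter the model only for small for gestational age and preterm delivery (SAP 4.2). Even where multiple gestation is a covariate, adjusting for it does not remove within-pair correlation.

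Two things are at stake: some extra false signals under the lower-limit rule, applied without multiplicity adjustment to neonatal death and 14 anomaly classes, and a reassuring upper limit that looks a little more precise than it is. One concordant twin pair can carry weight, because the adjusted analysis is allowed from five events in total.

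**Working it through.** **The plan's own figure.** SAP 3.3 states 95.7% power for a primary endpoint: 15,000 women per cohort, 1% incidence in the unvaccinated, true relative risk 1.25, margin 2, one-sided alpha 0.625%. A Miettinen-Nurminen type score calculation gives 95.71%, so the figure reproduces. It concerns primary endpoints, which are per woman or singleton-only, and this point does not touch it. The plan gives no event count, power or twin share for neonatal death or anomalies.

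**Inputs that must be assumed.**
- t, the share of pregnancies that are twins: 1% to 3%.
- k, the risk for a twin infant relative to a singleton: 1 to 1.5 for an anomaly class, 3 to 7 for neonatal death.
- c, the probability that the co-twin is affected given that one is: 0.05 to 0.5 for anomalies, 0.1 to 0.5 for neonatal death.

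**Formulas.**
- Share of affected infants who are twins: f = 2tk / (2tk + 1 − t).
- For a rare event, the count in a twin pair with risk q per infant has variance of about 2q(1 + c). The independent model takes 2q. The ratio of true to modelled variance is therefore D = 1 + f·c.
- Shortfall of the planned standard error: 1 − 1/√D.
- True one-sided rate of the signal rule: 1 − Φ(1.96/√D).

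**Results.**

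| Case | t, k, c | f | D | SE too small by | One-sided rate | Coverage |
|---|---|---|---|---|---|---|
| Neonatal death, low | 1%, 3, 0.1 | 0.057 | 1.006 | 0.3% | 2.5% | 94.9% |
| Neonatal death, high | 3%, 7, 0.5 | 0.302 | 1.151 | 6.8% | 3.4% | 93.2% |
| Anomaly class, low | 1%, 1, 0.05 | 0.020 | 1.001 | 0.05% | 2.5% | 95.0% |
| Anomaly class, high | 3%, 1.5, 0.5 | 0.085 | 1.042 | 2.1% | 2.75% | 94.5% |

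Example, neonatal death high: f = 2(0.03)(7) / [2(0.03)(7) + 0.97] = 0.42/1.39 = 0.302; D = 1 + 0.302 × 0.5 = 1.151; √D = 1.073; 1 − 1/1.073 = 6.8%.

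**Offset.** Poisson variance for a yes/no outcome is itself too large by a factor of about 1/(1 − p). At p = 2% the factor is 1.020, so the standard error is about 1.0% too wide (√1.020 = 1.010). That is comparable with the sibling effect for anomaly classes near 2%. At p = 0.2% it is only 0.1%, so it does nothing for neonatal death.

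**Simulation of the signal rule at a true relative risk of 1.** 15,000 women per cohort, unadjusted model, at least one event per cohort and five in total.

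| Singleton risk | t, k, c | Mean events, both cohorts | Planned model, twins correlated | Planned model, twins independent |
|---|---|---|---|---|
| Anomaly 0.5% | 1.5%, 1.5, 0.3 | 155 | 2.5% | 2.4% |
| Anomaly 1.5% | 2%, 1.5, 0.3 | 468 | 2.5% | 2.4% |
| Anomaly 1.9% | 3%, 1.5, 0.5 | 604 | 2.6% | 2.4% |
| Neonatal death 0.1% | 1.5%, 5, 0.3 | 34 | 2.5% | 2.3% |
| Neonatal death 0.2% | 1.5%, 5, 0.3 | 68 | 2.6% | 2.4% |
| Neonatal death 0.2% | 3%, 7, 0.5 | 83 | 3.2% | 2.3% |

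A separate simulation gave 2.3% to 2.6% in ordinary scenarios and 3.3% in the extreme neonatal-death scenario. With variance clustered on the mother, the rate was 2.0% to 2.5%.

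**The case against.** The strongest reply is that the effect is too small to matter. In ordinary scenarios the simulated rule runs at 2.5% to 2.6%. With independent twins it would run slightly below nominal, so the correlation mostly moves it to nominal. That stands for anomaly classes, and largely for neonatal death outside the extreme case.

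A second reply is that the plan accepts extra false signals. SAP 5.2 declines multiplicity adjustment so as not to miss a safety finding, and Protocol section 7 already asks for caution in reading the anomaly results. Both are true. But SAP 5.2 defends a choice about multiplicity; it does not address a variance that ignores sibling pairs.

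A reader might infer that Patient_ID must be the infant's own number, because the protocol says that "all infants born in KPSC hospitals are automatically assigned a MRN regardless of whether the mother is a current plan member". The documents do not establish that. SAP 4.2 leaves the identifier undefined, and SAP 3.2.4 and 5.1 use the word patient for the pregnant woman. If Patient_ID is the mother's, the robust option would already cluster siblings for any anomaly class above 2%. It would still not apply to neonatal death or to classes at or below 2%.

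Robust variance also has a cost. With very few events the sandwich estimate can be unstable, and for a class near 2% it removes the Poisson conservatism, so an interval could even narrow. This stands, and the fix needs a check beside it.

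**Conclusion.** The point holds, as a minor one. For neonatal death and for each anomaly class at or below 2% incidence, the planned variance treats siblings as independent, and no text provides for clustering on the mother. This follows from omission; the SAP nowhere asserts independence.

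The size rests wholly on the assumed twin share, risk ratio and concordance. For neonatal death the standard error is about 0.3% to 7% too small and the one-sided signal rate about 2.5% to 3.4%; the upper end needs all three inputs at their extremes. For anomaly classes the shortfall is at most about 2%, and Poisson conservatism may cancel part or all of it.

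A reader might conclude that the signal rule is seriously miscalibrated, or that the safety conclusions are in doubt. The figures do not support that. The error makes a false signal slightly more likely and does not hide harm, and the primary endpoints and their power are unaffected. Nor should the point be read as covering a relative risk for all anomalies combined: Table 5 plans anomalies by type and Table Shell 5 marks the overall relative risk as not applicable, although the text of SAP 4.3 mentions overall prevalence.

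**What to change.** In SAP 4.3 and Table 5, specify Poisson regression with robust variance clustered on the mother's pregnancy identifier (REPEATED subject = mother/pregnancy ID) for neonatal death and each anomaly class, whatever the incidence. State in SAP 4.2 that Patient_ID is the mother's identifier.

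Add one sensitivity analysis for these endpoints, either per mother (any affected infant) or restricted to singletons, to guard against unstable sandwich variance when events are few.

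The cost is a few SAP sentences and minor programming. Protocol 3.1 says the infant's record number is linked automatically to the record of a mother who is a current member, so the cluster variable should be to hand. The intervals will differ slightly and will usually be wider.

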### 3.2.4 Covariates

Covariates (Table 2) to be collected and explored include medical conditions indicative of a high-risk pregnancy and other relevant baseline characteristics. The algorithms for identification of high-risk medical conditions are described in the DMP.

Table 2. List of covariates (all covariates will be treated as categorical in the analyses)

High-risk medical condition
Thyroiditis (present/absent)
Diabetes (present/absent)
Other autoimmune diseases (present/absent)
Renal diseases(present/absent)
Cardiac diseases (present/absent)
Pre-pregnancy obesity (BMI>40: yes/no/missing)
Pre-existing hypertension (present/absent)
Rhesus sensitization (present/absent)
HIV infection (present/absent)
Syphilis infection (present/absent)
Cervical incompetence (present/absent)
Lifestyle factors
Smoking status from pregnancy start to index date (Yes/No)
Alcohol use from pregnancy start to index date (Yes/No)

Enrollment
Length of membership prior to 27 weeks gestation (but after pregnancy start) – having continuous membership from pregnancy start to index date (Yes/No)
Medicaid insurance (public health insurance: Indicator of low-income status) – any Medicaid enrollment from pregnancy start to index date (Yes/No)
Utilization
Health care utilization (receipt of medical care) from pregnancy start to index date
Any hospitalization or ED visit (Yes/No)
Number of outpatient visits (0-4/5-12/ $\geq 13$ )
Maternal Data
Number of previous pregnancies (0/1/ $\geq 2$ /Missing)
History of pregnancy loss (Yes/No)
Season of pregnancy start (September-March/April-August)
Vaccine
Receipt of other vaccines during pregnancy, e.g., influenza vaccine (Yes/No)
Receipt of vaccines containing diphtheria, tetanus toxoid or pertussis antigens within one year before pregnancy (Yes/No)
Matching variables
Race/Ethnicity (White/Black/Hispanic/Asian/Other)
Multiple gestation (Yes/No)
Age at pregnancy start (years)

Smoking status will be defined as current smoker or not. If patients reported they smoked any time from pregnancy start to index date, then they will be current smokers. Alcohol use will be defined in a similar fashion.

Length of membership prior to 27 weeks gestation (but after pregnancy start) will be defined as a dichotomous variable of having continuous membership (allowing up to a 31-day gap) from pregnancy start to index date.

Health care utilization will be defined as any hospitalization or emergency department (ED) visit, and number of outpatient visits (0-4, 5-12,  $\geq 13$ ) from pregnancy start to index date.

Receipt of other vaccines during pregnancy will be defined as any receipt of other vaccines from pregnancy start to index date.

The covariates included in adjusted analyses will be determined by scientific relevance, association with exposure and outcome, and data availability. Specifically, we will select covariates by following these steps:

1. The distribution of covariates will be reviewed. Those covariates in the same category with rare events will likely be combined as a single covariate. For example, we might consider grouping all chronic conditions into a single covariate.
2. The data availability will be checked. If a covariate contains a large proportion that is missing, and the proportion missing is differential by exposure, then the covariate may not be included.
3. Association of covariates with exposure will be assessed. We will use standardized difference to assess the balance of covariates between exposed and unexposed cohorts. Unlike p-values, for which magnitude is highly related to sample size, standardized difference is a unified approach to quantifying the magnitude of difference between groups regardless of sample size, where an absolute value less than 0.1 is considered a negligible difference (3). We will use a SAS macro %stddiff developed by PPD and PPD (4) to calculate the standardized differences for continuous and categorical variables. Potential confounders will be determined by absolute standardized difference (ASD)  $>0.1$ .
4. Association of potential confounders (identified from step 3) with each primary endpoint will be further assessed using a change-in-estimate approach (5). Diabetes, pre-existing hypertension (except for the analysis of the preeclampsia and/or eclampsia endpoint), Medicaid insurance, and health care utilization, which are considered as the most representative prognosis factors, will be kept in the adjusted model regardless of their association with exposure and primary endpoints. For a specific endpoint, the exposure coefficient estimate from a model adjusted for the 4 above covariates will be compared with the estimate from a model adjusted for one more covariate at a time. Covariates which result in a 10% change in the exposure coefficient estimate will be selected for final adjusted analysis.
5. All potential confounders (identified from step 3) will be included in the analyses of secondary endpoints. If the outcome is rare and the adjusted model cannot converge, problematic covariates will be removed from the model. If total counts from the two groups (i.e., sum of events in the exposed and unexposed cohorts) is less than 5, then no adjusted analysis will be performed.

